Post-treatment: Participants in the Altitudes condition will be asked to complete the battery of measures examining psychosocial constructs at the approximately 6-month timepoint (+/- 2 weeks). Specifically, Altitudes participants will be asked to complete the Experience of Caregiving Inventory (ECI; Szmukler), the Family Questionnaire of Expressed Emotion (Wiedemann et al., 2002), Brief COPE (Carver, 1997), UCLA Loneliness Scale (Russell, 1996), Multidimensional Scale of Perceived Social Support (For control and Alternative form for Altitudes condition; Zimet et al., 1990), Modified Psychosis Attitudes Survey (PAS; Kopelovich et al., 2022), PTSD Checklist for DSM-5 (PCL-5, Weathers et al., 2013), Post Traumatic Growth Inventory (PTGI, Tedeschi & Calhoun, 1996), General Health Questionnaire-12 (GHQ-12; Goldberg, 1972), Self-Compassion Scale – Short Form (SCS-SF; Raes et al., 2011), Five Facet Mindfulness Scale (FFMQ; Bohlmeijer et al., 2011) and aforementioned Altitudes platform brief questionnaires: the Altitudes Health Care Climate Questionnaire (A-HCCQ), Altitudes Usability Questionnaire (AUQ), and Altitudes Perceived Competence Scale (A-PCS), and Working Alliance Inventory for guided Internet interventions (WAI-I, Gomez Penedo et al., 2019). Participants will complete a brief survey on engagement with services within the CSC program and outside the program (e.g., individual therapy, family groups outside of CSC, etc.). They will also be asked to participate in a qualitative interview focusing on the experience of Altitudes and deeper understanding of acceptability and feasibility of the platform. Participants in the control condition will complete all the aforementioned measures except for the four brief Altitudes questionnaires and the qualitative interview.

Evaluations

Primary outcomes: Our primary objective is to examine the feasibility and acceptability of implementing Altitudes as a part of coordinated specialty care services provided by first-episode psychosis clinics across the state of North Carolina. We will examine site usage information as well as collect data on carers' perceptions of the platform to assess this outcome (e.g., its utility, approachability, and helpfulness).

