Secondary outcomes: Our second aim is to assess the extent to which carers engage with the platform (i.e., site usage information) is associated with improvements in expressed emotion, perceptions of caregiving, coping strategies, loneliness, social support, self compassion, mindfulness, and mood symptoms. We also plan to examine the associations between carers' involvement in Altitudes and their loved one with FEP's use of emergency services (e.g., ED visits). We will compare outcomes from the Altitudes and control groups to examine any improvements experienced by participants who engaged with the platform compared to routine clinical care.

Exploratory outcomes: We would like to explore rates of trauma symptoms related to experiencing and providing support for a loved one who experienced an initial psychotic episode. One of the exploratory aims is to examine the extent to which their loved one's initial psychotic episode and related experiences (e.g., psychiatric hospitalizations, changes in work/school engagement, etc.) might be associated with trauma-related symptoms. We are also interested in the extent to which engagement in Altitudes might promote post traumatic growth among caregivers of a young person with FEP. Trauma and post traumatic growth from caregivers in the treatment group will be compared to controls to assess the extent of impact of Altitudes on these outcomes.

Safety Evaluations

A safety plan for Altitudes was developed before participants joined the digital platform by research staff based on previous experience with digital interventions. All safety measures were approved by the director of each participating NC FEP clinic.

Statistical and Analytic Plan

Primary Outcomes: For Aim 1, we will use descriptive statistics to examine carers' perceptions of the Altitudes platform and clinical moderators via four brief questionnaires: the Altitudes Health Care Climate Questionnaire (A-HCCQ), Altitudes Usability Questionnaire (AUQ), Altitudes Perceived Competence Scale (A-PCS), and Working Alliance Inventory for Guided Internet interventions (WAI-I, Gomez Penedo et al., 2019). Additionally, descriptive statistics will assess interactions with the platform to evaluate acceptability and engagement (e.g., logins, posts, reactions, completed activities, etc.) with the platform (i.e., acceptability and usability).

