Information gathered in the post-treatment qualitative interview will be analyzed to identify participants' thoughts about the usefulness of Altitudes as well as feedback to improve the intervention for others. Qualitative analysis will be conducted on the feedback interviews using grounded theory. As with qualitative analysis, a codebook will be developed by the research team in which thematic analysis of all interviews will conducted. The codebook will include themes and subthemes with a focus on the different perceived strengths of the intervention as well as areas that need improvement.

Secondary Outcomes: The platform will collect information about frequency of engagement with Altitudes (i.e., site usage). Psychosocial outcomes will be summarized within and between conditions using univariate statistics (e.g., means, standard deviations). To evaluate change over time on psychosocial outcomes, we will utilize linear mixed models (LMM) including fixed effects of time, group, and group x time interactions and random effects at the participant level. We will calculate changes from baseline at each time point using least-squares means and standardized least-squares mean differences to estimate within- and between-group changes, respectively. To estimate magnitude of change from baseline, we will calculate effect sizes. We will explore the relationship between baseline characteristics (e.g., age, gender) and engagement data (i.e., site usage information) on any changes in psychosocial outcome measures from baseline to midpoint and posttreatment using multiple linear regression. We will use Pearsons correlation coefficients to examine associations between carers' involvement in Altitudes and their loved one with FEP's use of emergency services (e.g., ED visits). If possible based on sample size, we will dichotomize engagement data (site usage) between low engagement and high engagement before comparing site usage with emergency service utilization.

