As this platform will be provided as an adjunct to CSC clinical care, pertinent clinical impressions and other relevant clinical information will be shared with the individual's clinical team at their respective FEP clinic.

All individual interviews will be conducted virtually via secure Zoom and will be led by the Altitudes study coordinator and/or a graduate student in clinical psychology at UNC-Chapel Hill. All feedback sessions will be digitally recorded, and will be de-identified and transcribed by a member of the research team or a transcription service. The purpose of these recordings and transcriptions is to allow the research team to examine the feedback provided in the interviews for the purposes of improving the platform to better support families and caregivers in supporting their loved ones experiencing psychosis via psychoeducation and skills such as healthy coping mechanisms.

Subjects

Up to 30 total Altitudes participants will be recruited from two of the FEP clinics in North Carolina (OASIS & SHORE) as it is a pilot study, specifically family members of individuals experiencing FEP. An additional 30 control participants will be recruited from three other FEP clinics in North Carolina (Eagle, Encompass, and AEGIS). All participants will have a loved one currently enrolled in or recently graduated from a CSC program. Demographic and clinical information that will be collected as self-report for possible use as covariates includes: 1) participant demographics: age, sex/gender identity, race/ethnicity, level of education, current zip code, relationship to loved one, employment status, proximity to the loved one with psychosis (e.g., cohabitating, living in different states), hours of contact with loved one per week on average, number and ages of any other children; and 2) young person with psychosis' demographics and relevant clinical information: age, sex/gender identity, level of education, stage of recovery, and level of education.

Eligibility Criteria

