1. Descriptive statistics examining Site Usage Information [Time Frame: Duration of the trial, from onboarding at baseline through post-treatment]

The Altitudes platform passively collects engagement data, including the number of therapeutic pathways started and completed as well as any posts or comments made on the platform. We will provide mean and standard deviation scores for each site usage category, as well as a range, for the Altitudes group only. Depending on sample size, we will categorize users in low or high engagement groups.

2. Mean Change in UCLA Loneliness Scale Score [Time Frame: Baseline, Post-treatment, up to 14 weeks]

The UCLA Loneliness scale is a 20-item scale. Answers are on a 4-point scale with options "I often feel this way," "I sometimes feel this way," "I rarely feel this way," and "I never feel this way." Possible scores range from 20 to 80. Higher scores reflect worse outcomes (greater feelings of loneliness). The UCLA Loneliness Scale is a part of the PhenX Toolkit.

3. Mean Change in Multidimensional Scale of Perceived Social Support - total score [Time Frame: Baseline, Post-treatment, up to 14 weeks]; Alternative form for Altitudes participants, original form for control group.

The MOS Social Support Survey is a 16-item scale. Answers are on a 7-point scale with options ranging from "very strongly disagree" to "very strongly agree". Possible scores range from 16 to 112. Higher scores reflect higher feelings of social support (more perceived social support).

4. Mean Change in the Experience of Caregiving (ECI) Score [Time Frame: Baseline, Post-treatment, up to 14 weeks]

The Experience of Caregiving (ECI) Scale is a 66-item scale. Answers are on a 5-point scale starting at 0 with options "never," "rarely," "sometimes," "often," and "nearly always". Possible scores range from 0 to 264. Higher scores indicate greater feelings of preparedness for caregiving whereas lower scores reflect feeling less prepared to provide caregiving.

5. Mean Change in Family Questionnaire of Expressed Emotion - Total Score [Time Frame: Baseline, Post-treatment, up to 14 weeks]. The Family Questionnaire of Expressed Emotion is a part of the PhenX Toolkit.

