In addition, users will be able to "switch off" their profile and hide all of their existing comments on the system should they become concerned about their privacy during their course of participation. The limits of the moderator to respond (e.g., in a timely manner to emergencies) will also be fully explained. In order to protect the privacy of users who discontinue using the system, any accounts that have not been activated for one month may be deactivated following a follow-up telephone call from a moderator. Specifically, our disengagement protocol states that a participant will receive an email/call/text message if they have not logged onto the platform for two weeks. If another two weeks pass, we will call this person to check in about any potential issues or concerns. As noted

above, the moderation team will check in with participants on a monthly basis to ensure they are able to navigate the site with ease and to answer any questions they might have about the platform and any of its components/capabilities. Participants can opt out of these regular check ins from moderators at any time. If participants do not comply with the guidelines for safe use of Altitudes (e.g., discriminatory comments towards other users; disclosing identifying details of the identified patient) they will be excluded from the system.

Clinical safety: Although highly unlikely for the parent or caregiver, it is possible that participants may post information indicative of a clinical risk in their loved one, although participants will be advised that the service cannot respond to emergencies. Nonetheless, clinical risk will be monitored through manual and automated procedures. Information related to clinical risk will be screened daily by moderators and/or research staff. This information can include: 1) posts made by participants, which disclose evidence of deterioration in mental state of the young person in the care of participants; 2) participants reports or complaints on posts made by other users; and 3) automatically detected and blocked words posted by participants in the system. Additionally, clinical and family peer moderators will analyze the 'Community' feed to ensure that misinformation and falsehoods are not being spread by users of the platform.

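### Mean, SD and range may not describe typical platform use and cannot show how many carers did not use the platform; add median, IQR and number with zero use.

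*Combined protocol and SAP*

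**What the plan says.** The Data Analytic Plan (Secondary Outcome Measures, item 1) describes engagement data that the platform collects passively, "including the number of therapeutic pathways started and completed as well as any posts or comments made on the platform". The committed summary is: "We will provide mean and standard deviation scores for each site usage category, as well as a range, for the Altitudes group only". The next sentence adds: "Depending on sample size, we will categorize users in low or high engagement groups".

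The synopsis (Statistical and Analytic Plan) is more general. For the primary aim, "descriptive statistics will assess interactions with the platform to evaluate acceptability and engagement", with logins, posts, reactions and completed activities as examples. For the comparison with emergency service use it says: "If possible based on sample size, we will dichotomize engagement data (site usage) between low engagement and high engagement". Neither place gives a cut-point.

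On the role of these data, the synopsis (Evaluations, Primary outcomes) says of the feasibility and acceptability objective: "We will examine site usage information as well as collect data on" carers' perceptions. On numbers, the Subjects section says: "Up to 30 total Altitudes participants will be recruited from two of the FEP clinics in North Carolina". Carers set their own level of use and choose their own pathways.

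Three kinds of account status bear on the counts:

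- The Online safety section says that "any accounts that have not been activated for one month may be deactivated following a follow-up telephone call from a moderator".
- The same section lets a user hide their own profile and existing comments.
- The Withdrawal criteria allow an account to be suspended, or restricted so that the user can read content but not post.

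The plan does not say how such accounts are counted or whether they stay in the denominator. Nowhere does it name a median, an interquartile range, a number of non-users or a summary of use over time.

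**The concern.** Counts of posts, comments and pathways under self-directed use can be skewed, with some carers at zero and a few very active. In a group of 30 or fewer, a handful of heavy users can then pull the mean well above what most carers did. The range adds only the two extremes.

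The first question about feasibility is how many of the carers given the platform used it, and the protocol hypothesises that they will. If the usage results are a mean, an SD and a range, a reader could take moderate average use as evidence of general uptake when a minority supplied most of it.

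Account status adds a smaller ambiguity. A carer barred from posting and a carer who chose not to post both show zero posts. If deactivated accounts were dropped from the table, the mean would rise although nobody's use had changed.

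**Working it through.** The plan states no expected usage figure, no usage threshold and no power calculation, so there is no figure of its own to reproduce. Three checks were made.

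**1. Can mean, SD and range show the number of non-users?** This check assumes no distribution. The input is n = 30, the maximum in the Altitudes group. Take two constructed sets of counts:

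| | Set 1 | Set 2 |
|---|---|---|
| Counts | one 0, twenty-six 1s, two 10s, one 60 | nineteen 0s, one 1, nine 5s, one 60 |
| Sum | 26 + 20 + 60 = 106 | 1 + 45 + 60 = 106 |
| Sum of squares | 26 + 200 + 3600 = 3826 | 1 + 225 + 3600 = 3826 |
| Range | 0 to 60 | 0 to 60 |
| Median | 1 | 0 |
| Zero use | 1 of 30 (3%) | 19 of 30 (63%) |

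Mean = 106/30 = 3.53 for both. SD = √[(3826 − 106²/30)/29] = √[(3826 − 374.53)/29] = √119.02 = 10.91 for both. The planned summary is identical in all its parts, while one set shows nearly universal use and the other majority non-use. The median and the zero count separate them.

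**2. How far could the mean sit from the typical carer?** The documents give no distribution, so this is an illustration. Assumption: a negative binomial count with mean μ = 20 and dispersion k, so SD = √(μ + μ²/k) and P(0) = (k/(k + μ))^k. The top-3 share is the average over 20,000 simulated samples of 30.

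| k | SD | Median | Mean/median | P(0) | Share from top 3 of 30 |
|---|---|---|---|---|---|
| 0.3 | 36.8 | 5 | 4.0 | 28% | 51% |
| 0.5 | 28.6 | 9 | 2.2 | 16% | 42% |
| 1 | 20.5 | 14 | 1.4 | 5% | 32% |
| 2 | 14.8 | 17 | 1.2 | 1% | 25% |
| 5 | 10.0 | 19 | 1.05 | under 0.1% | 20% |

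Worked line for k = 0.5: SD = √(20 + 400/0.5) = √820 = 28.6; P(0) = (0.5/20.5)^0.5 = 0.156; mean/median = 20/9 = 2.2.

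The gap is large when skewness is strong and negligible when it is mild. The ratio runs from about 1.05 to 4 over this range of k.

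**3. What would an unstated denominator do?** Leaving z non-users out of 30 multiplies the mean by 30/(30 − z): 30/27 = 1.11 for z = 3, 30/24 = 1.25 for z = 6, and 30/20 = 1.50 for z = 10.

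**The case against.** The case against giving this much weight has several parts.

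- **Other summaries are planned.** A reader might infer that mean, SD and range are all there is. The documents do not support that: a low/high grouping follows in the next sentence, and the synopsis's open-ended descriptive statistics do not exclude a median. This stands. But the grouping is conditional, has no cut-point and does not isolate zero use, so it does not supply the missing count.
- **Skewness is not known.** A reader might infer that a few heavy users will dominate, or that the mean will be 2 to 4 times typical use. That holds only at the strongly skewed end of the assumed range. Pathways also come from a finite menu, so an unbounded count with mean 20 may not fit them. This stands, and 'may' is the right word.
- **The planned figures would give a warning.** In the assumed model at k = 0.3 and 0.5, the sample SD exceeds the mean in over 99% and 96% of samples of 30, and the minimum is 0 in over 99%. A reader would see skew and at least one non-user. This stands, but the number of non-users remains unknown.
- **Deactivation follows non-use.** It is discretionary, comes after a month of inactivity and a telephone call, and nothing shows that it would change cumulative counts much. This stands. It is also distinct from a profile hidden by the user, and the two should not be merged.
- **Feasibility does not rest on usage alone.** Site usage is listed as a secondary outcome and carries no threshold. The feasibility objective also draws on perceptions, recruitment, and safety and privacy. This stands and limits the consequence.

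**Conclusion.** The point holds in a limited form. The stated summary of site usage cannot tell a reader how many carers did not use a given feature: the same mean, SD and range are compatible with 3% or 63% non-users among 30. That result needs no distributional assumption.

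Whether the mean would also misstate typical use is open. Under the assumed negative binomial it could be about 5% above the median (k = 5) or four times it (k = 0.3), and nothing in the documents says where this trial will fall. The uncertainty is itself a reason to name a summary that works either way.

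The documents do not support the stronger conclusion that the feasibility result as a whole would be overstated. Only its usage component is affected, and no decision rule is tied to it. This is an inexpensive improvement in reporting, not a flaw that undermines the trial.

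**What to change.** In Secondary Outcome Measures, item 1:

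- Keep mean, SD and range. For each usage category add the median, interquartile range and n (%) with zero use, with all onboarded Altitudes carers as the denominator.
- Report n (%) of those carers active in each of months 1 to 6, and define 'active' in advance, for example as at least one login in the month.
- Report separately the number of accounts deactivated for inactivity, hidden by the user, and restricted or suspended. Keep all of them in the denominator, and state whether hidden comments are counted.
- If the low/high grouping is kept, state its cut-point before the data are examined.

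The cost is a few table rows, mostly from engagement data that the platform already collects. The documents do not say that changes of account status are logged, so a simple log with dates may have to be set up. The monthly activity count is a small added outcome. Carers have nothing further to complete.

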A-HCCQ	Altitudes Health Care Climate Questionnaire
A-PCS	Altitudes Perceived Competence Scale
AUQ	Altitudes Usability Questionnaire
CBT	Cognitive Behavioral Therapy
CSC	Coordinated Specialty Care
FEP	First Episode Psychosis
FFMQ	Five Facet Mindfulness Questionnaire
GHQ	General Health Questionnaire
NC	North Carolina
NSR	Non-significant Risk
OASIS	Outreach and Support Intervention Services
PAS	Psychosis Attitude Survey
PI	Principal Investigator
PSS	Peer Support Specialist
PTGI	Post-Traumatic Growth Inventory
PTSD	Post-Traumatic Stress Disorder
SCS-SF	Self Compassion Scale – Short Form
SHORE	Supporting Hope, Opportunities, Recovery and Empowerment
UCLA	University of California, Los Angeles
UNC-CH	University of North Carolina at Chapel Hill
WAI-I	Working Alliance Inventory – guided Internet interventions

PROTOCOL SYNOPSIS

Title

Altitudes for caregivers: A pilot study

Funding

This trial is funded by North Carolina Department of Health and Human Services & University of North Carolina at Chapel Hill

Clinical Phase

Pilot

Study Rationale

The purpose of the present study is to investigate the acceptability and feasibility of implementing a moderated online social media platform with therapeutic content, Altitudes, as a part of an adjunct services offered at first-episode psychosis (FEP) clinics across North Carolina, also known as coordinated specialty care (CSC) programs. Additionally, to further assess the secondary aim of impact on well-being, we will recruit a control group of caregivers.

Study Objective(s)

Examine the acceptability and feasibility of Altitudes at North Carolina (NC) FEP clinics as part of an adjunct clinical service through the following objectives:

- 1) Assessment of any changes in psychological measures across the six-month intervention
- 2) Ability to meet our recruitment targets
- 3) Evaluation of the safety and privacy protocol
- 4) Evaluation of the frequency and types of engagement on Altitudes

Study Design

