To evaluate the extent to which engagement in Altitudes may have impacted treatment participants' psychological health and perceptions of their social environment in comparison to the control group, all individuals will be asked to complete a battery of psychological measures at baseline, mid-treatment, and post-treatment visits. All measures will be administered by a member of the study team via secure Zoom. They will additionally complete a brief engagement measures on services they are accessing (e.g., services through the CSC program, individual therapy, group therapy at an outside organization, etc.).

At each of the three timepoints, all participants will be asked to complete the Experience of Caregiving Inventory (ECI; Szmukler), the Family Questionnaire of Expressed Emotion (Wiedemann et al., 2002), Brief COPE (Carver, 1997), UCLA Loneliness Scale (Russell, 1996), Multidimensional Scale of Perceived Social Support (For control and Alternative form for Altitudes condition; Zimet et al., 1990), Modified Psychosis Attitudes Survey (PAS; Kopelovich et al., 2022), PTSD Checklist for DSM-5 (PCL-5, Weathers et al., 2013), Post Traumatic Growth Inventory (PTGI, Tedeschi & Calhoun, 1996), General Health Questionnaire-12 (GHQ-12; Goldberg, 1972), Self-Compassion Scale – Short Form (SCS-SF; Raes et al., 2011), and Five Facet Mindfulness Scale (FFMQ; Bohlmeijer et al., 2011).

At baseline, all participants will be asked to complete a brief demographic questionnaire and answer a small number of clinical questions about their loved one (e.g., "Of the options provided below, what stage of recovery best describes your loved one?").

At midpoint, Altitudes condition participants will also be asked to provide their perceptions of the Altitudes platform and clinical moderators via four brief questionnaires: the Altitudes Health Care Climate Questionnaire (A-HCCQ), Altitudes Usability Questionnaire (AUQ), and Altitudes Perceived Competence Scale (A-PCS) and Working Alliance Inventory for guided Internet interventions (WAI-I, Gomez Penedo et al., 2019).

At posttreatment, Altitudes condition participants will be asked to participate in a qualitative interview focusing on the experience of Altitudes and deeper understanding of acceptability and feasibility of the platform.

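### Social support is measured with a different form in each arm at every visit, so a form effect cannot be separated from the group effect in the planned between-arm comparison

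*Combined protocol and SAP*

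**What the plan says.** The outcome definition (Data Analytic Plan, Secondary Outcome Measures, item 3) names mean change in the Multidimensional Scale of Perceived Social Support and adds "Alternative form for Altitudes participants, original form for control group". The scoring text beneath it begins "The MOS Social Support Survey is a 16-item scale", with a 7-point response scale and a range of 16 to 112. That is one scoring description, under a different instrument name, and it is not assigned to either form.

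The list of measures for the three timepoints (Research Design & Methods, Overview) has the same split: "Multidimensional Scale of Perceived Social Support (For control and Alternative form for Altitudes condition". So do the synopsis entries for each visit and the Baseline, Mid-Treatment and Post-Treatment Procedures.

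The arms are to be compared on this outcome. The Study Rationale says that "to further assess the secondary aim of impact on well-being, we will recruit a control group of caregivers". The synopsis names social support among the secondary outcomes and continues: "We will compare outcomes from the Altitudes and control groups to examine any improvements experienced by participants". The Statistical and Analytic Plan states: "Psychosocial outcomes will be summarized within and between conditions using univariate statistics". It then specifies "linear mixed models (LMM) including fixed effects of time, group, and group x time interactions and random effects at the participant level", with "standardized least-squares mean differences to estimate within- and between-group changes, respectively". No exception, shared-item score, linking step or caveat is given for the social support scale.

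**The concern.** Every Altitudes carer completes one form and every control carer the other, at every visit. Nobody completes both, and no shared items are identified. A difference between arms in total score could come from the platform, from the questionnaire, or from both, and analysis of the totals cannot tell these apart.

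This matters because the control group was added to assess impact on well-being, and the section on benefits to treatment participants lists social support as a possible gain. A between-arm difference on this scale, or its absence, could not be attributed with confidence to Altitudes rather than to the form. Allocation by clinic already limits attribution for every outcome. The form split is a further limit, specific to this scale and avoidable.

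**Working it through.** **Figures in the plan.** The plan gives no power calculation, SD or effect size to reproduce. The score range is consistent with its item count: 16 × 1 = 16 and 16 × 7 = 112.

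**Step 1: can form be separated from arm?** Take 30 + 30 carers at three visits. The fixed effects are an intercept, two time terms, group and two group-by-time terms: 6 columns, rank 6. Adding form and two form-by-time terms gives 9 columns, and the rank stays at 6. Form is fully aliased with group, and form-by-time with group-by-time.

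**Step 2: a constant offset.** Suppose the alternative form reads *a* points higher throughout, and both arms truly move from 50 to 55.

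- Difference between arms at 6 months: (55 + a) − 55 = a.
- Difference in change: [(55 + a) − (50 + a)] − (55 − 50) = 0.

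An offset of 5 or 10 points therefore appears in full in the between-condition means and the group term, and vanishes from change from baseline and from group-by-time.

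**Step 3: unequal item counts (illustration; all inputs assumed).** One form has 16 items and the other k = 14, 12 or 10. Either arm could have the shorter form, so either sign is possible. Both arms have the same true change per item, c = 0.25 or 0.5. The SD of the item-average score is s = 1.0 or 1.5, so the total-score SDs are 16s and ks.

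- Spurious difference in raw change: c × (16 − k).
- Pooled SD: s × √[(256 + k²)/2].
- Standardized size: c(16 − k) / {s√[(256 + k²)/2]}.

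| c | s | k = 14 | k = 12 | k = 10 |
|---|---|---|---|---|
| 0.25 | 1.0 | 0.033 | 0.071 | 0.112 |
| 0.5 | 1.0 | 0.067 | 0.141 | 0.225 |
| 0.25 | 1.5 | 0.022 | 0.047 | 0.075 |
| 0.5 | 1.5 | 0.044 | 0.094 | 0.150 |

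At k = 16 every entry is zero. If each arm is standardized by its own SD, the result is c/s − c/s = 0. The plan does not say which SD it will use.

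**Step 4: comparison with sampling error.** Assume a correlation ρ of 0.5 to 0.7 between baseline and follow-up and 30 complete, independent carers per arm. In pooled-SD units, SE = √[2(1 − ρ)] × √(2/30) = 0.258, 0.231 and 0.200 for ρ = 0.5, 0.6 and 0.7.

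The most extreme case is k = 10, c = 0.5, s = 1.0, ρ = 0.7:

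- Raw effect: 0.5 × 6 = 3.0.
- Raw SE: √0.6 × √[(256 + 100)/30] = 2.67.
- Ratio: 3.0/2.67 = 1.12.

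Changing the fixed SD used for scaling changes the effect but not this ratio, because the SE rescales with it: pooled 0.225/0.200, Altitudes at 16 items 0.188/0.167, control at 10 items 0.300/0.267. With 24 per arm and a design effect of 1.25 for relatives (both assumed), the pooled SE at ρ = 0.7 is 0.25, and the ratio falls to 0.225/0.25 = 0.90.

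**Step 5: equal counts, unequal responsiveness (assumed).** If one form registers 0.8 or 1.25 times the change of the other, with a common fixed SD, the size is c|1 − r|/s. For r = 0.8 this is 0.033 to 0.100, and for r = 1.25 it is 0.042 to 0.125.

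**The case against.** The strongest reply is that the named outcome is mean change and the planned between-group estimate is a standardized difference in change. Each carer keeps the same form, so a constant offset drops out. That stands. It does not cover the between-condition means or the group term, nor a difference in item count, content or responsiveness.

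A second reply is that the two forms may be equivalent. They may be, but no equivalence evidence or description of either form is given, and the single scoring paragraph can be read as covering both forms or only one.

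A third is that this is one secondary scale in an exploratory pilot allocated by clinic. That stands as a limit on severity. The between-group hypotheses under Outcomes concern coping, expressed emotion and understanding of psychosis. UCLA Loneliness, a related measure, has no arm-specific form, so a between-arm comparison of a related construct remains.

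A reader might infer more: that the comparison is biased, that it favours Altitudes, or that the alternative form asks about the platform itself. The documents support none of these, because they say nothing about how the forms differ or which, if either, is longer. Nor does the split invalidate the control comparison for the other outcomes.

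**Conclusion.** The concern holds as a question of identifiability: form is completely aliased with arm on this one scale, and the planned analysis does nothing to deal with it. That conclusion follows from the documents and needs none of the assumed inputs.

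The consequence is less certain. The size and direction of any form effect are unknown. In the item-count illustration the effect on standardized change runs from zero to about 0.22 in absolute value with a pooled SD, at most about 1.1 standard errors with 30 per arm. The milder responsiveness scenarios fall within that range. These figures are not upper bounds, since the true difference between the forms could be smaller or larger than assumed.

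Primary outcomes (Altitudes arm only), within-arm change and the other scales are not affected. This is a cheap improvement that should be made, at the lower end of priority.

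**What to change.** 1. State the item count, score range, scoring and content of each form, and reconcile the two scale names in Secondary Outcome Measures, item 3.
2. Use one score common to both arms for the between-arm mixed model and the between-condition means. If the alternative form contains identically worded original items, score those items in both arms. Otherwise give the original form to both arms at all three visits.
3. Report any Altitudes-only items within that arm.
4. State which SD standardizes the between-group difference.
5. If data are already collected and no common items exist, rely on the within-arm change already planned. Then either omit the between-arm contrast or label it descriptive with the form difference stated. Omitting it is a choice, not a necessity.

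The cost is scoring and analysis-plan wording if items are shared. Otherwise it is a change to the REDCap form and possibly a few extra items per visit for Altitudes carers. Their number cannot be given because neither form's content is described. In the case under item 5, the cost is at most one secondary between-arm contrast.
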